Methodology: *Criteria:* We will recruit couples where the Veteran partner is positive on VA primary care mental health screens who self-identify as in a committed relationship where one partner demonstrates significant relationship dissatisfaction. We will exclude partners with common contraindications for couples therapy or who are already engaged in family services. *Evaluation:* Partners will provide initial ratings of outcomes in separate baseline sessions. *Intervention:* Then couples will complete BRC in three 30-minute couple sessions. *Follow-up:* Partners will complete post-treatment assessments separately that include outcome measures packet and an open-ended interview.

Data Safety Monitoring Plan: This is a small pilot trial that will not use a data safety monitoring board. Safety will be monitored by the PI, Syracuse VA IRB, and Canandaigua Research Compliance Office (RCO) in consultation with the Information Security Officer (ISO).

Data Analysis: We will use descriptives (e.g., frequencies; means) and repeated measures ANOVA to analyze quantitative data. We will use framework-guided rapid analysis to analyze open-ended qualitative data.

List of Abbreviations

AUDIT-C – Alcohol Use Disorders Identification Test Consumption Questions

BRC - Brief Relationship Checkup

CDGA- Canandaigua VA Medical Center

C-SSRS - Columbia Suicide Severity Rating Scale

Doc # - Reference document Attached to IRB Application Package

EBP – Evidence Based Program

IBCT - Integrative Behavioral Couple Therapy

IPV – Intimate Partner Violence

ISO - Information Security Officer

MI – Motivational Interviewing

PC-MHI – Primary Care Mental Health Integration

PC-PTSD-5 – Primary Care PTSD Screener for DSM-5

PC-Screen – Primary Care Mental Health Screen (i.e., PHQ-2; PHQi9; AUDIT-C; PTSD-PC-5)

PHQ-2 – Physician Health Questionnaire 2-item Depression Screen

PHQi9 – Physician Health Questionnaire, Item 9 Suicide Ideation Screen

RC Questionnaire - Relationship Checkup Questionnaire

RCT - Randomized Control Trial

ROPC- Rochester Community Based Outpatient Clinic

VINCI – VA Informatics and Computing Infrastructure (VINCI)

VVC - VA Video Connect

Contents

Pro	otocol Title:	5
1.0	Study Personnel	5
2.0	Introduction	6
3.0	Objectives	7
4.0	Resources and Personnel	8
5.0	Study Procedures	9
5.	5.1 Study Design	9
5.	5.2 Recruitment Methods	14
5.	5.3 Informed Consent Procedures	16
5.	5.4 Inclusion/Exclusion Criteria	17
5.	5.5 Study Evaluations	18
5.	5.6 Data Analysis	19

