5.4 Inclusion/Exclusion Criteria

List of criteria for inclusion

- 1) Both partners must be age 18 or over
- 2) Both partners must demonstrate sufficient knowledge of English and cognitive capacity to understand the study through comprehension of consent questions
- 3) Both partners must self-identify as "in a committed relationship" with their partner for at least 6-months.
 - *Note:* Eligibility will NOT be based on marital/cohabitation status or sexual orientation to remain consistent with VA priorities of offering inclusive family services.
- 4) At least one partner must report at least mild relationship distress on a satisfaction screen (CSI-4<13.5)
- 5) At least one partner must have Veteran status
- 6) The Veteran partner must screen positive on at least one PC-Screen (i.e., PHQ-2 ≥3; PHQi9≥1; AUDIT-C≥5; OR PC-PTSD-5≥4)

List of criteria for exclusion:

- Either partner reports that they are engaged in ongoing couple or family therapy (via brief questions during Telephone Screen).
 Note: Any new couple/family therapy scheduled *after* screening will not impact eligibility and will be evaluated as an outcome.
- 2) Either partner reports severe intimate partner violence in the last year (via semi-structured interview during the Baseline session).
- 3) Either partner reports experiencing suicidal intent / attempts in the last month (via C-SSRS in Baseline session).
 - *Note:* Participants will NOT be excluded based on suicidal ideation or plan alone.
- 4) Either partner experiences current psychosis (via chart review, presentation during session, or MINI psychosis scale).
- 5) Either partner experiences current mania (via chart review, presentation during session, or MINI mania scale).

All staff will be trained in the semi-structured IPV interview, C-SSRS, P4, and MINI psychosis and mania scales to be used at any time they are concerned about individual functioning during either in-person sessions or phone sessions. Veteran charts will be reviewed prior to any Veteran-participants' to check for any indications of hospitalization or records flag. Results will be discussed with Drs. [name] or [name], licensed psychologists who will integrate findings to determine whether exclusion criteria are met.

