5.6 Data Analysis

Sample Size Determination

As the purpose of the present study is to primarily pilot the BRC intervention, we selected our target sample size based on our maximum expected capacity to run subjects through the protocol given our limited staff (2 couples/month) and the limited time in which to run the study (1 year).

Expected study continuation/lost to follow-up rate. We project 75% retention based on prior VA RCTs with couples.^{39,40} Thus, if we successfully recruit 20 couples, we expect to obtain complete data from 15 couples at follow-up.

Expected screen failures. As noted above, we expect that only 20% of Veterans screened will be both eligible and interested in participating in the larger study and that only 50% of partners will be eligible and interested. Thus, we are expecting 200 screen failures (i.e., approximately 160 Veterans and 40 Non-Vet partners).

Analytic Strategy by Aim

The Drs. [name] and [name] will maintain the database and conduct all analyses. Findings will be used for the preliminary study sections of a grant and, depending on data, in presentations or publications.

Aim 1: Evaluate the feasibility of BRC. Frequencies will be used to calculate the recruitment rate (i.e., # couples where both agree to attend the baseline/30-day period; Sub-aim 1-1) and completion rate (i.e., # completing all sessions/those completing baseline; Sub-aim 1-2). The above metrics will be calculated both across the sample and within recruitment source to estimate the feasibility of conducting a large-scale RCT in that population. To evaluate protocol adherence (Sub-aim 1-3), staff other than the therapists will evaluate randomly selected digital session recordings from each therapist using established criteria that rates elements of BRC delivery on a 1-5 scale.²⁶ Sufficient adherence is defined as 75% of elements rated at 4 or higher.

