Aim 2: Pilot outcomes. As relationship quality and emotional intimacy are dependent between partners, we will calculate effect size dyadically using a repeated measures ANOVA with Partner (Veteran-Supporting) and Time (pre-post) as within "subjects" factors to generate partial-η² (Sub-aim 2-1). In contrast, differential recruitment criteria will create baseline differences in suicide risk factors (Sub-aim 2-2) and efficacy discussing mental health (Sub-aim 2-3). Thus, we will calculate separate Cohen's *d* estimates for Veteran and Supporting partners. Effect sizes will then be contrasted with 1-month change in the above outcomes observed in past waitlist control studies of Veterans to inform power analysis. Finally, we will examine chart review data to investigate change in proportion of Veterans engaged in mental health services (Sub-aim 2-3). In cases where specific referrals were made in the final session, we will also assess the proportion utilizing those services.

Aim 3: Explore suitability of BRC. Mean scores will be calculated for each participant on the CSQ-8 and the WAI. Acceptability (Sub-aim 3-1) is defined as 75% of participants scoring ≥3 on both measures. We will use framework-guided rapid analysis (RA) to evaluate semi-structured interviews.⁵⁸ Transcription services will be provided through VA HSR&D's Centralized Transcription Service Program (CTSP). The audio recordings to be transcribed by CTSP staff will not contain any identifiable information and will only be labeled with a study identification number. They will be saved in a project folder shared between IRB-approved study staff and CTSP transcription staff that is located on the VA secure V: drive. IRB-approved study staff will place the audio files into the shared folder for a CTSP transcriptionist to have access for the purposes of transcription. Once the audio file is transcribed, the transcriptionist will save the completed transcript in the same shared folder using the same identification number. No data (audio files, in process transcripts, or completed transcripts) will leave the VA secure server. As

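### Partial-η² is the only effect size named for relationship satisfaction and intimacy, and alone it cannot support the planned contrast with waitlist change

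*Combined protocol and SAP*

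**What the plan says.** Section 5.6 (Aim 2) gives a reason for a dyadic model: partners' scores on satisfaction and intimacy are not independent. It continues: "we will calculate effect size dyadically using a repeated measures ANOVA with Partner (Veteran-Supporting) and Time (pre-post) as within" factors, and the stated product is the effect size, with these "factors to generate partial-η² (Sub-aim 2-1". Cohen's d, separately for each partner, is introduced as the different approach for suicide risk factors (Sub-aim 2-2) and for efficacy in discussing mental health (Sub-aim 2-3). The exploratory paragraph extends d to further risk factors, but not to satisfaction or intimacy.

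The use of the estimates follows directly: "Effect sizes will then be contrasted with 1-month change in the above outcomes observed in past waitlist control studies of Veterans to inform power analysis". This covers all the outcomes just listed, so it includes Sub-aim 2-1.

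Two other places bear on the point. The Abstract says, in general terms, "We will use descriptives (e.g., frequencies; means) and repeated measures ANOVA to analyze quantitative data". Sample Size Determination in section 5.6 says "we expect to obtain complete data from 15 couples at follow-up". The protocol does not say that SDs, pre-post correlations, between-partner correlations or confidence intervals will be reported for Sub-aim 2-1. It also does not say which ANOVA term the partial-η² belongs to.

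**The concern.** A comparison with waitlist change needs a direction and a size on a scale that the other studies share. Partial-η² is a proportion of variance and fails this in three ways:

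- Improvement and deterioration of equal size give the same value.
- It cannot be negative, so its average is above zero even when nothing has changed. At 15 couples this is not negligible.
- For a fixed change in SD units, it rises with the pre-post correlation and falls as partners' scores become more correlated. Two studies with the same change can therefore report very different values.

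Satisfaction and intimacy are the direct targets of the intervention. If partial-η² is what goes forward for them, the power input for the RCT rests on correlations that nobody has stated.

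**Working it through.** **Inputs from the protocol.** Target 20 couples and 75% retention (section 5.6). The plan's own figure reproduces: 20 × 0.75 = 15 couples with complete data. The protocol gives no partial-η², d or correlation.

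**Assumed inputs.** Pre-post correlation r = 0.5, 0.8 or 0.9; between-partner correlation ρ = 0 or 0.5; equal SDs; the same change d (in individual-SD units) in both partners; cross-partner, cross-time correlation rρ. The Time main effect is taken as the term of interest.

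**Step 1: no change.** Time has F(1, 14), so partial-η² = F/(F + 14), which follows a Beta(1/2, 7) distribution. Its mean is 0.5/7.5 = 1/15 = 0.067, its median 0.033 and its 95th percentile 0.247.

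**Step 2: a 0.30-SD change.** One partner's change has variance 2(1 − r). Under the assumptions above, the two partners' changes correlate at ρ, so the couple-average change has variance (1 − r)(1 + ρ). Hence

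- dz = d / √[(1 − r)(1 + ρ)]
- t² = 15 dz²
- partial-η² = t² / (t² + 14)

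Example with r = 0.5, ρ = 0: dz² = 0.09/0.5 = 0.18, t² = 2.7, partial-η² = 2.7/16.7 = 0.162.

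| r | ρ | Converted partial-η² | Simulated mean estimate |
|---|---|---|---|
| 0.5 | 0 | 0.162 | 0.196 |
| 0.8 | 0 | 0.325 | 0.338 |
| 0.9 | 0 | 0.491 | 0.492 |
| 0.5 | 0.5 | 0.114 | 0.157 |
| 0.8 | 0.5 | 0.243 | 0.266 |
| 0.9 | 0.5 | 0.391 | 0.398 |

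The last column is the mean over 100,000 simulated 15-couple datasets per row. Because d enters only as d², a change of −0.30 gives the same converted values; in the simulation, +0.30 and −0.30 agreed to within 0.001.

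**Step 3: the reverse reading.** Suppose partial-η² = 0.20 is observed. Then t² = 14 × 0.20/0.80 = 3.5, t = 1.871 and |dz| = 1.871/√15 = 0.483. The absolute change is 0.483 × √[(1 − r)(1 + ρ)]:

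| r | ρ = 0 | ρ = 0.5 |
|---|---|---|
| 0.5 | 0.342 | 0.418 |
| 0.8 | 0.216 | 0.265 |
| 0.9 | 0.153 | 0.187 |

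One reported value therefore fits 0.15 to 0.42 SD, in either direction.

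**Step 4: what that spread means for power (illustration only).** Treat the figure as the net difference between arms, for individuals, with two-sided 5% alpha and 80% power. Then n per arm = 2(1.960 + 0.842)²/d², which is 698 at d = 0.15 and 89 at d = 0.42.

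**Step 5: precision of the signed alternative.** The half-width of the 95% CI for couple-average change is t(0.975, 14) × √[(1 − r)(1 + ρ)]/√15, with t(0.975, 14) = 2.145. For r = 0.5, 0.8 and 0.9 this is 0.392, 0.248 and 0.175 SD at ρ = 0, and 0.480, 0.303 and 0.214 SD at ρ = 0.5.

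**The case against.** The strongest reply is that the harm arises only if partial-η² travels alone. Sub-aim 2-1 is to calculate change, the Abstract promises means, and a two-by-two ANOVA is built on four cell means, so the analysts will see whether satisfaction rose or fell. That is fair: mistaking a decline for a gain is unlikely. But means supply direction only. They do not give a standardised change without an SD, or the variance of change without the correlations, and the general line on descriptives ties none of these to Sub-aim 2-1.

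A second reply is that a one-degree-of-freedom partial-η² converts to |dz|, which already reflects the variance of change that a repeated measures RCT needs. This is also true. Yet |dz| is still unsigned and still depends on the correlations, so it does not give change in scale points or baseline-SD units. The protocol does not say in what metric the waitlist studies report, so the difficulty of a conversion cannot be judged from it. The plan also leaves undefined which Cohen's d it means for the other outcomes; a paired version would depend on the pre-post correlation too, though it would keep its sign.

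Third, the width of the range depends on assumed inputs. The top values need r = 0.9, whereas section 5.1 allows up to three months from baseline to finish. With r limited to 0.5 to 0.8, an observed 0.20 still fits 0.22 to 0.42 SD, about a twofold spread.

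Finally, imprecision at 15 couples may matter more than the metric. At r = 0.5 the expected interval around a 0.30-SD change includes zero, since both half-widths (0.392 and 0.480) exceed 0.30. This stands, and limits what the fix can achieve. No test, progression rule or sample size within this pilot depends on partial-η², and the missing quantities can be computed later from the same data.

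**Conclusion.** The concern holds. The plan names a specific metric for its two main relationship outcomes and then assigns it a use for which that metric alone is unsuited. The absence of a sign and the positive average under no change (0.067 at 15 couples) need no assumed correlations. The size of the correlation dependence does: 0.114 to 0.491 for the same 0.30-SD change, or 0.15 to 0.42 SD for the same observed 0.20. Those ranges assume equal SDs, equal change in both partners and that Time is the term meant.

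The dyadic ANOVA is not invalid, and the reason given for it is sound. The gap lies in what is carried forward from it. It is worth correcting because informing the later trial is the pilot's stated purpose and the correction is cheap.

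**What to change.** Keep the dyadic ANOVA. In section 5.6, Aim 2:

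- Name signed mean change (post minus pre) as the effect size for the waitlist contrast, for Veterans, for supporting partners and for the couple average, with 95% CIs.
- Give it in scale points first, then in baseline-SD units, stating which SD is used. Entry requires that at least one partner "must report at least mild relationship distress on a satisfaction screen (CSI-4<13.5", which affects the baseline SD in this sample and so the comparability of SD units with other studies.
- Report the baseline and change SDs, the pre-post correlation and the between-partner correlation beside it.
- Keep partial-η² as a secondary descriptor if wanted, and say which ANOVA term it refers to.

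The cost is analysis wording only: the same data, visits and model. The visible price is wide intervals, with half-widths of about 0.18 to 0.48 SD over the assumed correlations, so the effects will look less certain. Changing the metric shows that imprecision but does not remove it.

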3.0 Objectives

Insights from the present study will inform the feasibility of a randomized control trial (RCT) of a refined, Veteran-specific Brief Relationship Checkup (BRC)¹⁵ by pursuing following aims:

Aim 1: Evaluate feasibility of conducting a BRC trial in Veterans with mental health concerns.

Sub-aim 1-1 Calculate recruitment rate (# couples with both partners consenting/30-day period)

Sub-aim 1-2 Calculate completion rate (# completing all activities/couples initiated)

Sub-aim 1-3 Evaluate providers' adherence to treatment protocol within this population.

Aim 2: Pilot outcomes that can be used to evaluate pre-post change in future studies of BRC.

Sub-aim 2-1. Calculate change in relationship functioning (i.e., relationship satisfaction, intimacy).

Sub-aim 2-2. Calculate change in suicide risk factors (i.e., depression, interpersonal needs, presence and intensity of ideation).

Sub-aim 2-3. Calculate change in treatment utilization (i.e., Veterans in treatment via chart review; Supporting Partners reported efficacy in discussing treatment/mental health).

Aim 3: Inform continued refinement of BRC to be suitable to the needs of Veterans and their partners.

Sub-aim 3-1. Evaluate acceptability of current BRC format (i.e., client satisfaction and working alliance).

Sub-aim 3-2. Identify areas for refinement using open-ended interviews.

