5.5 Study Evaluations

Questionnaires

See Table 1 for full list of measures. Except for newly developed measures, all measures have established reliability/validity and were selected with preference for measures used in VHA care.

Inclusion/Exclusion. The listed measures will assess eligibility (per Section 5.4). The relationship quality screen and PC-Screens are established short forms used in VA practice.

Safety. In addition to routine use to evaluate exclusion measures

Outcomes (Aim 2). We selected measures of relationship quality and depression used in weekly assessments for VA EBPs.²⁶ Intimacy and interpersonal risk will be assessed using well-validated measures. We are piloting new measures about communication around mental health.

Evaluation (Aim 3). The well-established acceptability measures are supplemented with open-ended interview questions to identify unique strengths and weaknesses of the program *Risk.* Measures assess shared risk factors for suicide and divorce to contextualize findings.

Table 1List of Measures used in Study										
Construct	Measure	Items	Purpose	Screen	Base	Tx	Post			
Demographics	Standard Items	8	Inclusion	X						
Relationship Status	Made for Study	4	Inclusion	X						
Tx Engagement	Made for Study	6	Exclusion	X						
Veteran Status	Standard Items	5	Inclusion	X						
IPV Assessment	VA IPV Screen	8	Safety		X		Xa			
Severe IPV Behaviors	IPV Interview	8	Exclusion/Safety		(X)	(X)	(X) ^a			
IPV Monitoring	IPV Session	1	Safety			Х				
Mania/Psychosis	MINI ²⁵	20	Exclusion		(X)	(X)	(X)			
Last Month Suicide Ideation Severity	C-SSRS ²⁷	5	Exclusion/ Safety		Х		Х			
Suicide Risk Eval	P4 Screener	4	Safety	(X)	(X)	(X)	(X)			
Relationship Quality	CSI ²⁸	4/32	Aim 2-1	Xb	Х		Х			
Intimacy	PRI	16	Aim 2-1		Х		Х			
Recent (2-Week) Depression	PHQ-9 ²⁹	2/8	Aim 2-2	Xp	Х		Х			
Recent Suicidal Ideation	PHQ-i9 ²⁹	1	Aim 2-2	X	Х		Х			
Last Month Ideation Intensity	C-SSRS ²⁷	5	Aim 2-2		X		Х			
Interpersonal Connection	INQ ³⁰	15	Aim 2-2		X		Х			
Discussing Mental Health	Made for Study	18	Aim 2-3		Х		Х			
Service Utilization	Chart Review	N/A	Aim 2-3				Х			
Perceived Quality of Service	CSQ-18 ³¹	8	Aim 3-1				Xa			
Quality of Alliance w/ Provider	WAI-SR ³²	12	Aim 3-1				Xa			
Semi-Structured Interview	Made for Study	15	Aim 3-2				Х			
Potential PTSD	PC-PTSD-5 ³⁴	6	Inclusion	X						
Trauma Exposure	LEC-5 ³⁵	17	Risk		X					
Childhood Adversity	ACES ³⁶	17	Risk		X					

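### Cohen's d by partner role is the only summary section 5.6 names for suicidal ideation; with about 15 couples it may be undefined or set by one or two people

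*Combined protocol and SAP*

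**What the plan says.** Section 3.0 states Sub-aim 2-2 as "Calculate change in suicide risk factors (i.e., depression, interpersonal needs, presence and intensity of ideation"). Table 1 in section 5.5 tags two ideation measures to this sub-aim: a single PHQ item labelled "Recent Suicidal Ideation" and five C-SSRS items labelled "Last Month Ideation Intensity". Both are taken at baseline and after treatment. The table also lists C-SSRS last-month ideation severity at both times, but only for exclusion and safety.

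Section 5.6, Aim 2, argues that "differential recruitment criteria will create baseline differences in suicide risk factors", and so plans separate Cohen's d "estimates for Veteran and Supporting partners". It does not say which standard deviation goes in the denominator, how presence is coded, or what is reported if every score is zero. The resulting effect sizes are to be set against changes seen in earlier waitlist groups of Veterans, to inform power for the larger trial. Aim 2 does plan a change in a proportion, but only for Veterans' use of mental health services. The exploratory analyses reuse the d approach and are meant to speak to tolerability and safety.

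The abstract adds a general line: "We will use descriptives (e.g., frequencies; means) and repeated measures ANOVA to analyze quantitative data".

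**The concern.** A standardised mean difference needs spread in the scores. When most people score zero at both visits, the standard deviation is either zero, so that d does not exist, or comes from one or two people, so that d describes them and not the group.

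Section 5.4 makes this a realistic prospect. Only the Veteran must be positive on a primary care screen. Any one of the four screens is enough, so even a Veteran need not report ideation. Recent intent or attempt excludes either partner, which trims the top of the range.

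Suicide prevention is the stated rationale of the study, and the effect sizes are meant to inform the power of the next trial. A d set by one person cannot do that. It also hides the results a reader would want first: how many people's ideation resolved, persisted or newly appeared.

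**Working it through.** **Number of complete pairs.** Section 5.6 gives 20 couples and 75% retention: 20 × 0.75 = 15, which matches the plan's figure. Each role therefore contributes about 15 paired scores. The plan gives no target d, alpha or power, so there is no power figure to reproduce.

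**Chance of an empty baseline.** The documents give no ideation rate, so prevalence p is an assumption shown as a range.
- No one with ideation among 15: (1 - p)^15
- At most one: (1 - p)^15 + 15p(1 - p)^14

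| Assumed p | None of 15 | At most one of 15 |
|---|---|---|
| 2% | 74% | 97% |
| 5% | 46% | 83% |
| 10% | 21% | 55% |
| 20% | 3.5% | 17% |
| 30% | 0.5% | 3.5% |

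The second column is the chance that d is undefined only if the baseline SD is the denominator.

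**Other denominators.** Assume further that ideation present at baseline persists in 60%, and newly appears in 2% of those without it. Treat ideation as present or absent.
- Pooled pre/post SD is zero when nobody has ideation at either visit: [(1 - p) × 0.98]^15 = 55%, 34%, 15% and 2.6% at p = 2%, 5%, 10% and 20%.
- SD of change is zero when nobody changes: [0.6p + 0.98(1 - p)]^15 = 66%, 55%, 41% and 22% at the same rates.

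If nobody reports ideation at either visit, d is 0/0 under all three choices.

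**One person decides the result.** Suppose one of 15 scores s at baseline and 0 afterwards, and the other 14 score 0 both times.
- Mean change = -s/15.
- SD of change = baseline SD = s/√15.
- d = (-s/15)/(s/√15) = -1/√15 = -0.26.
- With the pooled SD, √[(s²/15 + 0)/2] = s/√30, so d = -√30/15 = -0.37.

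The score s cancels. A drop from 1 and a drop from 25 give the same d, and the value depends on a denominator that the plan does not name.

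**What counts give instead.** With n = 15, exact 95% intervals are 0 to 21.8% for 0/15, 0.2 to 31.9% for 1/15, 1.7 to 40.5% for 2/15 and 4.3 to 48.1% for 3/15. These are wide, but they exist even when every score is zero.

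**The case against.** The best defence is that this is a small descriptive pilot, and the plan does not say that d excludes other summaries. A reader might infer that d is the only summary planned anywhere for ideation. The abstract's general mention of frequencies and means does not support that. Still, the line is not tied to ideation, and section 5.6 names only d for Sub-aim 2-2.

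A reader might also infer that presence will be analysed as yes/no. The sub-aim's wording suggests it, but the PHQ item has an entry cut of 1 or more, which points to a graded score, and its coding for Aim 2 is not stated. A d can be computed on either form when scores vary. The floor problem applies to both.

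The low rate is an inference. At least one partner must report relationship distress, which section 2.0 calls a suicide risk factor. Section 7.0 allows both partners to be Veterans, and ideation or a plan alone does not exclude anyone. At 20% prevalence an empty baseline is unlikely. Nor are Supporting Partners free of mental health assessment: the exclusions for intent or attempt, psychosis and mania apply to either partner. What they do not need is a positive primary care screen.

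Finally, the waitlist comparison concerns Veterans, so the Supporting Partner d matters less for power. That stands. The same formulas apply to Veterans at whatever rate they have, and their entry criteria do not guarantee ideation.

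**Conclusion.** The point holds in a limited form. For ideation, the one summary named in section 5.6 may be undefined, or may be set by one or two people, when about 15 pairs per role are available. The documents do not support saying that it will be undefined. That depends on a prevalence they do not give and a denominator they do not specify. Across assumed rates of 2% to 20%, the chance of an empty baseline runs from 74% down to 3.5%, and the chance of at most one person with ideation from 97% down to 17%. The single-case result, d of about -0.26 or -0.37 regardless of severity, needs no prevalence assumption, but it does assume that exactly one person has ideation and that it resolves.

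Depression and interpersonal needs, under the same sub-aim, are not affected. Severity is modest: the pilot is descriptive, but its effect sizes are meant to inform a later trial.

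**What to change.** In section 5.6, Aim 2:

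- Keep d for the PHQ depression items and the INQ, and name the standard deviation used.
- For presence of ideation (PHQ item 9 of 1 or more; any last-month C-SSRS ideation), report by role the paired counts (resolved, persistent, new, never) and the proportion at each visit with an exact interval. For Veterans, add the paired difference in proportions.
- For C-SSRS intensity, report by role the median, range and numbers improved or worsened across all participants. Do not restrict this to a subgroup defined by post-treatment ideation, because that conditions on the outcome and would often leave very few people.
- State that an ideation d will not be used for the later trial's power when it rests on only a few participants.

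Table 1 already schedules the needed measures at both times, so the cost is a few sentences and one small table. The C-SSRS severity row would also need Aim 2-2 added to its purpose. The downside is that ideation will have no single standardised effect size.
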